### 18.6.3. ABNORMAL INVOLUNTARY MOVEMENT SCALE (AIMS)

The AIMS is a clinician-rated assessment of abnormal movements consisting of unobtrusive observation of the subject at rest (with shoes removed) and several questions or instructions directed toward the subject. It contains seven items related to: facial, lip, jaw, and tongue movements (items 1 - 4), upper and lower extremity movements (items 5 - 6), and trunk movements (item 7). Three other items assess the subject at a global level (items 8 - 10), and two items assess dental status (items 11 - 12).

AIMS is assessed at these study visits: Visit 1E (coinciding with Visit 9 of SEP380-301), Visit 2E, Visit 4E, Visit 6E, Visit 8E, Visit 10E, Visit 12E, and Visit 14E.

The (non-global) AIMS total score is the sum of items 1 through 7. (Items 8 through 12 are not used in AIMS total score calculation.) The possible range for AIMS total score is 0 to 28. Higher values of the AIMS total score indicate increased severity in abnormal movement. If one or more of the 7 items contributing to AIMS total score calculation are missing at a visit, the total score will be set to missing for that visit.

AIMS total score at each visit is classified as 'abnormal' if: either at least two items (out of items 1 - 7) have a response of 'Mild' or higher (i.e., item score  $\geq 2$ ); or at least one item (out of items 1 - 7) has a response of 'Moderate' or higher (i.e., item score  $\geq 3$ ). Otherwise, the non-missing AIMS total scores is classified as 'normal'.

Item 8 of AIMS represents the global severity score. Post-Baseline AIMS global severity scores will be classified as 'worsened', 'unchanged', or 'improved', relative to a subject's Baseline response to item 8. A higher score than that of the Baseline would be classified as 'worsened'. Conversely, a lower score would be classified as 'improved'. If the score is equal to that of Baseline, the score will be classified as 'unchanged'. Relative to DB Baseline, the classification will be made for each OLE study visit. Relative to OL Baseline, the classification will be made for each post-OL Baseline extension study visit.

The DB Baseline and OL Baseline AIMS total score and global severity score will be derived as described in Section 7.2. The change from DB Baseline and OL Baseline in AIMS total score and global severity score will be derived as described in Section 7.7.

The observed values of AIMS total score and global severity score at both the DB Baseline and the OL Baseline, and at each scheduled OLE study visit (starting from Visit 2E) and LOCF, will be summarized descriptively.

descriptively.

Changes from DB Baseline in AIMS total score and global severity score will be summarized for each scheduled OLE study visit (starting from Visit 1E) and LOCF. Changes from OL Baseline will be summarized for each scheduled post-OL Baseline extension study visit (starting from Visit 2E) and LOCF.

Shift in AIMS total score category (Normal/Abnormal) from DB Baseline to each scheduled OLE study visit (starting from Visit 1E), LOCF, and the overall post-OL Baseline extension period (including both the OLE treatment period and the OLE follow-up period up to and including 7 days post the last OLE dose) will be summarized descriptively. Similarly, shift from OL Baseline in AIMS total score category to each scheduled post-OL Baseline extension study visit (starting from Visit 2E), LOCF, and the overall post-OL Baseline extension period will be summarized descriptively.

Frequency distribution of the AIMS global severity item will be summarized descriptively for DB Baseline, OL Baseline, each scheduled OLE study visit (starting from Visit 2E), and LOCF.

Changes in AIMS global severity score relative to DB Baseline (Worsened/Unchanged/Improved) will be summarized descriptively for each scheduled OLE study visit (starting from Visit 1E) and LOCF; changes relative to OL Baseline will be summarized descriptively for each scheduled post-OL Baseline extension study visit (starting from Visit 2E) and LOCF.

#### **18.6.4. BARNES AKATHISIA RATING SCALE (BARS)**

The BARS is a rating scale geared toward assessment of neuroleptic-induced akathisia, though it can be used to measure akathisia associated with other drugs as well. The BARS consists of four items, including one item assessing objective restlessness (item 1), two items targeting subjective restlessness (awareness and related distress; items 2 - 3), and one global clinical assessment of akathisia item (item 4). The objective and subjective items are anchored and utilize a 4-point scale. The global assessment item has a 6-point scale (from absence of akathisia through severe akathisia).

BARS is assessed at these study visits: Visit 1E (coinciding with Visit 9 of SEP380-301), Visit 2E, Visit 4E, Visit 6E, Visit 8E, Visit 10E, Visit 12E, and Visit 14E.

The BARS total score is the sum of items 1 through 3 and ranges from 0 to 9. Higher values of the BARS total score indicate higher severity of akathisia. If one or more of items 1 to 3 are missing at a visit, the BARS total score will be set to missing for that visit.

The post-Baseline BARS Global Clinical Assessment of Akathisia responses will be classified as 'worsened', 'unchanged', or 'improved', relative to a subject's Baseline response to this item. A higher score than that of the Baseline would be classified as 'worsened'. Conversely, a lower score would be classified as 'improved'. If the score is equal to that of Baseline, the score will be classified as 'unchanged'. Relative to DB Baseline, the classification will be made for each OLE study visit. Relative to OL Baseline, the classification will be made for each post-OL Baseline extension study visit.

The DB Baseline and OL Baseline BARS total score and BARS item scores will be derived as described in [Section 7.2](#). The change from DB Baseline and OL Baseline in BARS total score and BARS item scores will be derived as described in [Section 7.7](#).

The observed values of BARS total score at both the DB Baseline and the OL Baseline, and at each scheduled OLE study visit (starting from Visit 2E) and LOCF, will be summarized descriptively.

Changes from DB Baseline in BARS total score will be summarized for each scheduled OLE study visit (starting from Visit 1E) and LOCF. Changes from OL Baseline will be summarized for each scheduled post-OL Baseline extension study visit (starting from Visit 2E) and LOCF.

Changes in BARS global clinical assessment score relative to DB Baseline (Worsened/Unchanged/Improved) will be summarized descriptively for each scheduled OLE study visit (starting from Visit 1E) and LOCF; changes relative to OL Baseline will be summarized descriptively for each scheduled post-OL Baseline extension study visit (starting from Visit 2E) and LOCF.

### 18.6.5. MODIFIED SIMPSON-ANGUS SCALE (MSAS)

The MSAS is a clinician-rated assessment of neuroleptic-induced Parkinsonism consisting of 10 items. Items are anchor-based, rated on a 5-point scale (ranging between 0 and 4), and address rigidity, gait (bradykinesia), tremor, akathisia, shoulder shaking, glabellar tap, and salivation.

MSAS total score is defined as the sum of all 10 items and ranges between 0 and 40. Lower values of the MSAS total score indicate milder symptoms. If one or more of the MSAS items are missing at a visit, the MSAS total score will be set to missing for that visit.

The MSAS total score at each visit will be classified as 'abnormal' if it exceeds 3 (Rush, et al., 2000). Otherwise, the non-missing MSAS total score will be classified as 'normal'.

MSAS is assessed at these study visits: Visit 1E (coinciding with Visit 9 of SEP380-301), Visit 2E, Visit 4E, Visit 6E, Visit 8E, Visit 10E, Visit 12E, and Visit 14E.

The DB Baseline and OL Baseline MSAS total score will be derived as described in [Section 7.2](#). The change from DB Baseline and OL Baseline in MSAS total score will be derived as described in [Section 7.7](#).

The observed values of MSAS total score at both the DB Baseline and the OL Baseline, and at each scheduled OLE study visit (starting from Visit 1E) and LOCF, will be summarized descriptively.

Changes from DB Baseline in MSAS total score will be summarized for each scheduled OLE study visit (starting from Visit 1E) and LOCF. Changes from OL Baseline will be summarized for each scheduled post-OL Baseline extension study visit (starting from Visit 2E) and LOCF.

Shift in MSAS total score category (Normal/Abnormal) from DB Baseline to each scheduled OLE study visit (starting from Visit 1E), LOCF, and the overall post-OL Baseline extension period (including both the OLE treatment period and the OLE follow-up period up to and including 7 days post the last OLE dose) will be summarized descriptively. Similarly, shift from OL Baseline in MSAS total score category to each scheduled post-OL Baseline extension study visit (starting from Visit 2E), LOCF, and the overall post-OL Baseline extension period will be summarized descriptively.

### 18.6.6. PHYSICIAN'S WITHDRAWAL CHECKLIST (PWC)

Potential withdrawal effects will be assessed by the clinician using the PWC after completion of all scheduled effectiveness and safety assessments and procedures at Visit 14E (EOT/ET) and Follow-up (Visit 15E).

The PWC scale includes 20 symptoms and each symptom is assessed on a 4 point scale using the following: 0=Not Present, 1=Mild, 2=Moderate and 3=Severe. The score for each question is summed to compute a total score ranging from 0 to 60. If the response to any question is missing, then the total score will be missing.

The PWC total score will be summarized using descriptive statistics by visit and treatment group.

The frequency distribution of the PWC will be tabulated at Visit 14E and Follow-up.

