15.4.3.8. Physician's Withdrawal Checklist (PWC)

The PWC related summary will be based on the follow-up population. The PWC score will be summarized by presenting descriptive statistics of observed values and changes from Visit 14E (Month 12/EOT) by analysis group. Numbers and percentages of subjects with any new symptom or worsened old symptom for any PWC score or each individual symptom score will be provided by analysis group as well.

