### **3.2.2. OTHER SAFETY ENDPOINTS**

- The incidence of AESI including but not limited to hyperprolactinemia-related AEs
- Clinical laboratory evaluations (serum chemistry, hematology, thyroid panel, urinalysis)
- Clinical evaluation (vital signs including orthostatic effects, and 12-lead ECG measurements)
- Changes in prolactin values
- Changes in metabolic parameters (insulin, glucose, hemoglobin A1c (HbA1c), lipid panel)
- Change and percent change in body weight
- Change in body mass index (BMI)
- Incidence of treatment-emergent mania, defined as a YMRS total score  $\geq 16$  at post-Baseline visit (scheduled or unscheduled), or an adverse event of hypomania or mania
- Changes from Baseline in movement disorders scales: AIMS, BARS, and modified SAS
- Frequency and severity of suicidal ideation and suicidal behavior using the C-SSRS
- Change from Week 52/EOT (end of treatment) visit to the safety follow-up visit on the PWC

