### **3.2.3. EFFECTIVENESS ENDPOINTS**

- Changes in MADRS total score
- Changes in CGI-BP-S depression score
- The proportion of subjects with treatment response, defined as  $\geq 50\%$  reduction from Baseline in MADRS total score
- The proportion of subjects meeting criteria for remission, defined as MADRS total score  $\leq 12$
- Changes in HAM-A total score

- Changes in QIDS-SR16 total score
- Changes in SDS total and subscale scores (work/school, family, and social function)
- The proportion of subjects meeting criteria for functional remission, defined as having a score  $\leq 2$  on each of the SDS subscale scores (work/school, family, and social function)
- Changes in the EQ-5D-5L Visual Analog Scale (VAS) and Index scores
- Changes in the SHAPS total score

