## 7.5. WINDOWING CONVENTIONS

No visit windowing will be performed during the analysis for this study. Data will be analyzed according

to the schedule outlined in the CSP. However, with the exception of SAE and PWC, any data collected beyond 7 days post the last OLE dose will be excluded from the efficacy and safety analyses unless otherwise specified; these data will be presented in data listings only.

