#### **17.1.7. CHANGES FROM DB BASELINE AND FROM OL BASELINE IN SDS TOTAL SCORE AND SUBSCALE SCORES AT EACH SCHEDULED VISIT**

The Sheehan Disability Scale (SDS) is a subject-reported assessment of function. The SDS is a composite of 3 items designed to measure the extent to which 3 major sectors in a patient's life are impaired by depressive symptoms. This anchored visual analogue scale uses spatiovisual, numeric, and verbal descriptive anchors simultaneously to assess disability across 3 domains: work, social life or leisure activities, and home life or family responsibilities. The subject will rate his or her degree of impairment in each of these domains using an 11-point scale ranging from 0-10, with higher scores indicating more impairment. There are verbal descriptors for the points on the scale as well as numerical scores that provide more precise levels of the verbal descriptors. Scores for the 3 items are summed into a single dimensional measure of global functional impairment that ranges from 0 (unimpaired) to 30 (highly impaired).

SDS is assessed at these study visits: Visit 1E (coinciding with Visit 9 of SEP380-301), Visit 4E, Visit 6E, Visit 8E, Visit 10E, Visit 12E, and Visit 14E.

The DB Baseline and OL Baseline SDS total score will be derived as described in [Section 7.2](#). The change from DB Baseline and OL Baseline in SDS total score will be derived as described in [Section 17.1.7](#).

The observed values of SDS total score at both the DB Baseline and the OL Baseline, and at each scheduled OLE study visit (starting from Visit 1E) and LOCF, will be summarized descriptively.

Changes from DB Baseline in SDS total score will be summarized for each scheduled OLE study visit (starting from Visit 1E) and LOCF. Changes from OL Baseline will be summarized for each scheduled post-OL Baseline extension study visit (starting from Visit 4E) and LOCF.

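### Three endpoints listed in the SAP have no matching analysis in its text: PWC change from EOT to follow-up, SDS subscale changes, and SDS functional remission

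*SAP*

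**What the plan says.** **PWC.** SAP 3.2.2 lists as a safety endpoint "Change from Week 52/EOT (end of treatment) visit to the safety follow-up visit on the PWC". Protocol 15.4.3.8 plans "descriptive statistics of observed values and changes from Visit 14E (Month 12/EOT) by analysis group", and also "Numbers and percentages of subjects with any new symptom or worsened old symptom", for any PWC score and for each individual symptom. SAP 18.6.6 specifies two outputs: "The PWC total score will be summarized using descriptive statistics by visit and treatment group" and "The frequency distribution of the PWC will be tabulated at Visit 14E and Follow-up". Neither is a change, and neither compares a subject's follow-up answers with that subject's own EOT answers. SAP 4.7 says that the PWC keeps its follow-up summary and will use the Safety population. It says nothing about the change score or the symptom counts.

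**SDS.** SAP 3.2.3 lists changes in the total and in the three subscales, and also "The proportion of subjects meeting criteria for functional remission", meaning a score of 2 or less on every subscale. The heading of SAP 17.1.7 names total and subscale scores. Its text refers only to the total, for example "Changes from DB Baseline in SDS total score will be summarized for each scheduled OLE study visit". Functional remission is not mentioned anywhere in Section 17.

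**The concern.** Potential withdrawal symptoms after stopping the drug are a stated safety objective (SAP 3.1.2). The question is about individuals: did a subject who was free of a symptom at the end of treatment have it a week later, or have it more severely? Two separate visit summaries do not answer that. Similar averages, or even a falling average, are compatible with some subjects having developed new symptoms.

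For the SDS, a programmer who follows the text of 17.1.7 would produce the total only. Two listed effectiveness endpoints would then have no specified output, and a reader of the study report would find no explanation in 4.7.

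**Working it through.** The plan gives no figure on this point, so there is nothing to reproduce. The check sets listed endpoints against analysis text and then asks what separate visit summaries can recover.

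**1. Endpoint against analysis**

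| Listed endpoint | Protocol analysis | SAP analysis | Entry in SAP 4.7 |
|---|---|---|---|
| PWC change, EOT to follow-up (SAP 3.2.2) | 15.4.3.8: change from Visit 14E, plus new/worsened symptom counts | 18.6.6: total by visit, plus frequency distribution by visit | Population only |
| SDS subscale changes (SAP 3.2.3) | 15.4.2: general rule for continuous effectiveness measures | 17.1.7: named in heading, total only in text | None |
| SDS functional remission (SAP 3.2.3) | None specific to it (endpoint in 6.2) | None | None |

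**2. Could another SAP section supply the PWC change?** SAP 7.7 defines change from DB Baseline and from OL Baseline only. The schedule in SAP Appendix 7 has no PWC at Visit 1E; it is first done at Visit 14E. The general rule therefore never produces an EOT-to-follow-up change. The other multi-visit scales (MADRS, CGI-BP-S, HAM-A, QIDS-SR16, SDS total, EQ-5D-5L, SHAPS, YMRS, AIMS, BARS, MSAS) each have an explicit sentence on changes. The PWC does not.

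**3. Can two frequency tables give the new-symptom count?** Assume 64 subjects have both checklists (64 is the number enrolled in SAP 4.4, used here only as a scale) and that a symptom is present in k of them at each visit. Let a be the number with it at both visits. The number with a new symptom is k − a, and a can lie anywhere from max(0, 2k − 64) to k.

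- k = 8: new symptom in 0 to 8 subjects (0% to 12.5%)
- k = 16: 0 to 16 (0% to 25%)
- k = 32: 0 to 32 (0% to 50%)

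The two tables look the same across each whole range, even when every subject returns.

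**4. Can two visit summaries give the spread of the change?** With equal SD at both visits and correlation ρ, SD of change = visit SD × √(2 − 2ρ). For ρ = 0, 0.5, 0.8 and 0.9 the multiplier is 1.41, 1.00, 0.63 and 0.45. The visit summaries do not contain ρ.

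**5. Can they give the mean change?** Only if the same subjects contribute to both visits. Suppose N subjects have an EOT/ET checklist, m of them do not return, and at EOT the non-returners' mean exceeds the returners' mean by d. Then:

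difference in visit means = mean paired change − (m/N) × d.

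The documents give neither m nor d. With the assumed values m = 14, N = 64 and d = ±4 points, the distortion is 14 × 4/64 = 0.875 points: a false improvement if non-returners score higher at EOT, a false worsening if they score lower. Size and direction are unknown in advance.

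**6. SDS.** In SAP 17.1.7 the sentences on derivation, observed values and change all name the total score. MADRS response and MADRS remission each have their own section (17.1.3 and 17.1.4) with an indicator rule and a summary. Functional remission has neither.

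**The case against.** The strongest reply is that these are descriptive outputs in a study without inference, cut short at 64 enrolled subjects, and that everything needed is collected. The endpoints remain listed. SAP Section 9 says that separately provided templates govern table content. Section 4.7 claims only to list the main changes. All of this is fair and it limits the weight of the point. It does not supply the missing analysis: the templates are not among the documents, and the SAP is where an endpoint's derivation should be found.

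Four stronger readings are tempting, and the documents do not support them.

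- *The endpoints will never be computed or reported.* That cannot be known without the templates. What can be said is that the SAP text does not specify them. The heading of 17.1.7 suggests incomplete drafting of the subscales rather than a decision to remove them.
- *Functional remission was silently dropped from the protocol's analysis.* Protocol 15.4.2 has no analysis specific to it; the nearest text is the general sentence in 15.4 that categorical variables are tabulated. It is an endpoint left without a specified analysis in both documents.
- *The PWC exemption in SAP 7.5 ("with the exception of SAE and PWC, any data collected beyond 7 days post the last OLE dose will be excluded") is what lets an off-drug early-termination checklist serve as the reference.* SAP 7.4 maps early-termination data only when taken within 7 days of the last dose. A checklist on days 1 to 7 would be mapped with or without the exemption, and a later one is not mapped. The exemption has an evident use: Visit 15E falls 7 ± 2 days after the last dose, so checklists on days 8 and 9 would otherwise be lost. Neither document has a rule tying the reference checklist more closely to the last dose, and this point does not depend on one.
- *Pairing is needed for precision.* Treating the visits as independent overstates the standard error, because returners are a subset of those seen at EOT. With assumed values of 64 at EOT, 50 returning and SD 6, the SE of the difference in visit means is √(36/64 + 36/50 − 2r × 36/64) = 0.91, 0.78 and 0.62 for r = 0.4, 0.6 and 0.8. The paired SE is √(2 × 36 × (1 − r)/50) = 0.93, 0.76 and 0.54. The gain is small, and at r = 0.4 there is none. The case for pairing is that it answers the listed question.

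**Conclusion.** The point holds as a specification gap affecting three listed endpoints. It is firmest for the PWC: the protocol planned the within-subject change and the new/worsened counts, the SAP still lists the change as an endpoint, and the outputs in 18.6.6 cannot yield either result. SAP 4.7 does not disclose the difference. The SDS subscale gap is an unfinished section. Functional remission needs an analysis written for the first time.

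The conclusion rests on the text alone. The 0-to-16 range and the 0.875-point distortion show what separate summaries cannot settle, under assumed inputs; they are not predictions for this trial. The gap biases no planned estimate and affects no test. It should be closed because a stated safety objective depends on the PWC result and the remedy costs very little.

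**What to change.** **SAP 18.6.6.** Add the change in PWC total from Visit 14E (EOT/ET) to Visit 15E in subjects with both assessments, with their number. Add the number and percentage of those subjects with any new or worsened symptom, overall and by symptom. Keep the by-visit summaries.

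**SAP 17.1.7.** Add observed values and changes from DB and OL Baseline for the three subscales. Add the number and percentage of subjects with all three subscales at 2 or less, at each scheduled SDS visit and LOCF. State how a missing subscale is handled, in line with 17.2.

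**SAP 4.7.** If any of these outputs is meant to be omitted, list it there with the reason.

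**Cost.** A few table rows from data already collected. The paired PWC summary will include fewer subjects than the by-visit summaries, which is why its denominator should be shown.

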## 19. PHARMACOKINETIC ANALYSIS

All PK analysis will be performed using Safety population.

Blood sample for plasma concentrations of R-amisulpride, S-amisulpride, total amisulpride, and/or plasma prolactin measurement will be collected at: Visit 1E (coinciding with Visit 9 of SEP380-301), Visit 2E, Visit 4E, Visit 6E, Visit 8E, Visit 10E, Visit 12E, Visit 14E, and Visit 15E/Follow-up. Any plasma concentration or summary statistics below the lower limit of quantification (LLOQ) will be represented by "BLQ" (below the limit of quantification) in tables and listings. Amisulpride plasma concentration will not

be presented for the placebo group.

R-amisulpride, S-amisulpride, total amisulpride, and plasma prolactin concentrations at each scheduled sample collection time point (including ET and Follow-up, see [Section 7.4](#) for mapping of the ET visit) will be summarized descriptively (n, mean, median, minimum, maximum, coefficient of variation [CV] and if appropriate, geometric mean and geometric CV [GCV]). In addition, if there is at least 1 concentration < LLOQ within a treatment group at a time point, it will be set to  $\frac{1}{2}$  LLOQ for summary statistics calculations. Number and percentage of concentrations that are below the LLOQ will be provided for each visit. All PK summaries will be presented.

Population PK analysis methods will be used to characterize the PK/PD profiles in subjects treated with SEP-4199 CR. Analysis methods and results of population PK and PD analysis will be described in a separate document from the SAP and clinical study report.

